### **9.2 The Number of Participants**

Power calculation for sample size: Based on data from Landorf et al. regarding FHSQ, a sample size was calculated to detect a clinically important difference between groups of 13 (SD = 26.9) points in Foot Health Status Questionnaire scores using the pain sub-domain as the primary outcome, giving a required minimum sample size of 54 participants in each group plus 5% drop out rate = 57 per group. Total sample size n=114.

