## 6. TRIAL DESIGN

### 6.1 Summary of Trial Design

#### Type of Trial summary:

A single centre, double blinded, randomised controlled trial comparing the effectiveness of two methods of foot shape capture currently used in NHS Orthotic services in Scotland. This is an Interventional, equivalence trial using medical devices (insoles).

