### **9.0.2 Hypotheses**

We aim to evaluate the method of manufacturing CAD/CAM insoles from a direct-scan, compared to that of a foam-box cast. The null hypothesis is that the change in FHSQ Pain score pre and post-treatment will not differ between the treatment groups. The alternative hypothesis is that the change in FHSQ pain score will differ between groups.

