### **9.1 Description of Statistical Methods**

The change in FHSQ scores for the sub-domains of Pain, Foot Function, Foot Health and Footwear, will be compared between groups at the specified data collection time points: baseline, 4-weeks, 8-weeks and 12-weeks, using mix methods Analysis of Variance or Friedman tests with post hoc Wilcoxon tests for within group analysis and Mann-Whitney U tests for between group analysis if the data are not normally distributed.

The change in OPUS scores for the sub domain of Satisfaction With Device, will be compared between groups at the specified data collection time point of 12-weeks, using unpaired t-tests or Mann-Whitney U tests if the data are not normally distributed.

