### **9.3 The Level of Statistical Significance**

Significance will be considered at P<0.5

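### The trial is declared an equivalence trial, but its hypotheses and tests are those of a difference test: no margin or confidence-interval rule is given, the only significance level is printed as P<0.5, and the sample size states no power, alpha or sidedness

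*Combined protocol and SAP*

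**What the plan says.** - **Design.** The synopsis gives an equivalence design, and section 6.1 repeats it: "This is an Interventional, equivalence trial using medical devices (insoles"). Section 4 describes the doubt to be settled as whether the two capture methods yield insoles that work equally well.
- **Hypotheses (9.0.2).** "The null hypothesis is that the change in FHSQ Pain score pre and post-treatment will not differ between the treatment groups", and "The alternative hypothesis is that the change in FHSQ pain score will differ between groups".
- **Analysis (9.1).** FHSQ scores are compared "at the specified data collection time points: baseline, 4-weeks, 8-weeks and 12-weeks", by analysis of variance, or by Friedman and Wilcoxon tests with "Mann-Whitney U tests for between group analysis if the data are not normally distributed". No margin, paired one-sided tests or confidence-interval rule appears here or elsewhere.
- **Sample size (9.2).** The aim is to "detect a clinically important difference between groups of 13 (SD = 26.9) points", "giving a required minimum sample size of 54 participants in each group plus 5% drop out rate = 57 per group". Power, alpha and sidedness are not stated, nor whether 26.9 is the SD of the score or of its change.
- **Level (9.3).** "Significance will be considered at P<0.5". No other section gives a level.
- **Section 5** cites a minimal important difference of 12.5 points for change in pain, but does not call it an equivalence margin.

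**The concern.** In an equivalence trial the null is that the groups differ by at least a stated margin, and the data must reject it. Section 9.0.2 has this the other way round. Rejecting its null would show a difference; failing to reject it would show nothing. The plan therefore has no route to the conclusion the trial is designed to reach. The likely practical error is that a non-significant test is reported as showing that scan and cast are interchangeable.

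Three gaps make this worse. The printed level is implausible and nothing else in the documents corrects it. The primary time point is not explicit. The sample size cannot be traced to a stated test, so a reader cannot tell which question 54 per group was meant to answer.

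**Working it through.** **Inputs.** Difference 13 and SD 26.9 (9.2); 54 per group, 57 after 5% dropout (9.2); 1:1 allocation (6.4.4). Alpha, power, sidedness and margin M are not in the documents, so every value used for them below is an assumption. The calculations treat pain as a single endpoint compared by t-test, with 26.9 as the SD of the analysed outcome. Section 9.1 plans repeated-measures methods, so the results are approximate.

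**1. Reproducing 54.** The normal formula is n = 2 × (SD × (z_alpha + z_power) / d)², with 2 × (26.9/13)² = 8.563.

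| Assumption | z values | Normal n | Exact t n |
|---|---|---|---|
| Difference, one-sided 5%, 80% power | 1.645 + 0.842 | 52.9 | 54 |
| Difference, two-sided 5%, 70% power | 1.960 + 0.524 | 52.9 | 54 |
| Difference, two-sided 5%, 80% power | 1.960 + 0.842 | 67.2 | 69 |
| Equivalence, M = 13, 5% each side, 80%, beta not split | 1.645 + 0.842 | 52.9 | 54 |
| Equivalence, M = 13, 5% each side, 80%, beta split | 1.645 + 1.282 | 73.3 | 75 |

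Three rows return 54. The first does not fit the non-directional alternative in 9.0.2. The fourth fits the declared design but overstates equivalence power, because with a true difference of 0 the type II error must be shared between the two sides. The documents do not say which was used. The printed 0.5 does not explain 54 either: two-sided, 80% power would need 8.563 × (0.674 + 0.842)² = 19.7, about 20 per group. The dropout step is right: 54/0.95 = 56.8, so 57.

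**2. What a non-significant result would mean.** At 54 per group, SE = 26.9 × √(2/54) = 5.18.

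- Two-sided 5% critical difference: 1.983 × 5.18 = 10.26 points. Any smaller observed difference is non-significant.
- Power for a true 13 points is 70% (73% at 57), so such a difference is non-significant about 30% of the time.
- At a literal two-sided 0.5, the critical difference would be 0.677 × 5.18 = 3.5 points.

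**3. What equivalence would require.** The 90% CI half-width at 54 per group is 1.659 × 5.18 = 8.59. The observed difference must lie within 12.5 − 8.59 = 3.91 points if M is 12.5, or 13 − 8.59 = 4.41 if M is 13. Power of two one-sided t-tests at 5% each, true difference 0:

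| M | 54 per group | 57 per group |
|---|---|---|
| 12.5 | 55% | 59% |
| 13 | 60% | 64% |

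Power reaches 80% at M of about 15.3 with 54 per group, or about 14.8 with 57.

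**4. Sensitivity to the meaning of 26.9.** Suppose it is a score SD, with baseline correlation r (assumed; none is given), at 54 per group.

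- Unadjusted change, SD = 26.9 × √(2(1 − r)): for r = 0.3, 0.5 and 0.7 the two-sided 5% power for 13 points is 56%, 70% and 90%, and equivalence power at M = 12.5 is 30%, 55% and 85%.
- Baseline-adjusted, SD = 26.9 × √(1 − r²), r = 0.5: SD 23.3, difference power 82%, equivalence power 74% (M = 12.5) or 78% (M = 13).

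**The case against.** Three points can be made for the plan, and each stands in part.

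First, 54 is a legitimate answer to some question, and baseline adjustment or a wider margin could make it adequate. That is true. A reader might infer that the sample size is miscalculated or that the trial is underpowered. The documents support neither: 54 reproduces under several assumption sets, and the power for equivalence depends on a margin, an SD definition and a correlation that are not given.

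Second, P<0.5 is very probably a misprint. A reader might infer that the trial will really declare significance at 0.5; that is unlikely, and the 3.5-point figure only illustrates the literal text. The level still has to be corrected, because nothing else in the documents supplies it.

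Third, it would go too far to say that the plan gives no indication of a primary time point. The pre- and post-treatment wording in 9.0.2, with 12 weeks as the last follow-up, suggests baseline to 12 weeks. The fair criticism is that this is not explicit, since 9.1 lists four occasions.

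None of these supplies the missing margin or decision rule.

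**Conclusion.** The point holds and must be fixed. The contradiction between the declared equivalence design and the difference-test hypotheses and analysis is on the page and needs no assumption: as written, the plan cannot conclude equivalence. The level in 9.3 is wrong as printed, and 9.2 does not say what 54 per group was calculated to achieve.

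The numerical consequences are conditional on the single-endpoint t-test and SD 26.9 for the analysed outcome. On that basis a true 13-point difference goes undetected about 30% of the time at two-sided 5%, and equivalence power at 54 to 57 per group is 55% to 59% for M = 12.5 and 60% to 64% for M = 13. Those two margins are illustrations taken from the plan's own figures, not margins the plan adopts. How large any shortfall is, or whether there is one, remains open.

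**What to change.** No participants need be added.

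1. **9.3.** Replace P<0.5 with the intended level (presumably 0.05) and state sidedness.
2. **9.0.2.** Null: the between-group difference in change in FHSQ pain is at or beyond ±M points. Alternative: it lies within ±M.
3. **9.1.** Primary analysis: the between-group difference in change in FHSQ pain from baseline to one named time point (12 weeks, if that is what post-treatment means), with a 90% CI. Equivalence is concluded only if the whole CI lies within ±M. If the data are not normal, use a CI on the same points scale, such as Hodges-Lehmann. State that non-significance in a difference test is not evidence of equivalence.
4. **Timing of M.** Justify M on clinical grounds, not to reach a power, and fix it before any between-group comparison, masked or unmasked. Under Code-Breaking in 6.4.4 the two groups are analysed before they are identified. An equivalence verdict depends on the size of the difference, not its direction, so even a masked comparison would show enough to guide the choice of M.
5. **9.2.** State alpha, sidedness, what SD 26.9 refers to, and the power for equivalence within ±M at 54 to 57 evaluable per group. Stop describing 54 as the minimum needed unless that power supports it.

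**Cost.** Four short sections are reworded, and the sponsor must decide on M and the time point. The stated power becomes less favourable if M is near 12.5 to 13. Because the primary hypothesis and decision rule change, this is likely a substantial amendment to be submitted under 12.3. Version 2.0 (08/09/2022) predates the planned recruitment start (29/09/2022); the documents do not show the later status. If any between-group comparison, masked or not, has already been made, report the change as a deviation under 9.6.

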### **9.3 The Level of Statistical Significance**

Significance will be considered at P<0.5

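### Section 9.3 sets the significance level at 0.5, almost certainly a slip for 0.05, and no section states sidedness or power

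*Combined protocol and SAP*

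**What the plan says.** Section 9.3 is a single sentence: "Significance will be considered at P<0.5". It is the only significance level or confidence level anywhere in the document.

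Section 9.0.2 sets a null of no between-group difference in the change in FHSQ pain, and adds: "The alternative hypothesis is that the change in FHSQ pain score will differ between groups". That is non-directional, but the section does not say that testing is two-sided.

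Section 9.1 applies the threshold widely: "The change in FHSQ scores for the sub-domains of Pain, Foot Function, Foot Health and Footwear, will be compared between groups" at baseline and three follow-up times, by a mixed analysis of variance or rank tests. OPUS satisfaction is compared at 12 weeks.

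Section 9.2 opens with "Power calculation for sample size". It takes "a clinically important difference between groups of 13 (SD = 26.9) points" on the pain sub-domain and arrives at "54 participants in each group plus 5% drop out rate = 57 per group", then "Total sample size n=114". It gives no significance level, no sidedness and no power.

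**The concern.** A threshold of 0.5 is ten times the conventional 0.05. It is the rule by which every comparison in section 9.1 would be judged, and nothing elsewhere in the document corrects it. Followed as written, about half of all comparisons with no true difference would be declared significant. Section 9.6 requires deviations from the statistical plan to be described and justified, so quietly using 0.05 at analysis would itself be a deviation from the written plan.

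Section 9.2 adds a second gap. Because it omits the level, sidedness and power behind its calculation, correcting the digit in 9.3 does not tell the reader how well powered the trial is.

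**Working it through.** **Inputs.** From section 9.2: difference δ = 13, SD σ = 26.9, 54 per group before dropout, 5% dropout, 57 per group after. From section 9.3: α = 0.5. Power and sidedness are not in the document, so the values below are assumptions, tried over a range.

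**Method.** Two-sample t-test with equal groups. Standardised difference d = 13 / 26.9 = 0.483. The normal approximation for n per group is 2 × [(z₁ + z₂) / d]², where z₁ is the normal quantile for α (or α/2 if two-sided) and z₂ the quantile for power. The results below use the exact t-test, which differs slightly. This checks section 9.2 only. It is not the power of the mixed analysis of variance or rank tests in 9.1, and 9.2 does not say whether the SD is of scores or of change.

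**Step 1: the dropout allowance.** 54 / 0.95 = 56.8 and 54 × 1.05 = 56.7. Both round up to 57, and 2 × 57 = 114, so this step reproduces.

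**Step 2: which settings give 54?**

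| α | Sides | Power | n per group | Rounded up |
|---|---|---|---|---|
| 0.5 | two | 80% | 18.3 | 19 |
| 0.5 | two | 90% | 32.03 | 33 |
| 0.5 | two | 95% | 45.6 | 46 |
| 0.05 | one | 80% | 53.6 | **54** |
| 0.05 | two | 70% | 53.8 | **54** |
| 0.05 | two | 80% | 68.2 | 69 |

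The normal approximation gives 19.7 (20) in the first row, because it ignores the opposite tail, which is not negligible at α = 0.5. The conclusion is the same.

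The printed 0.5 does not lead to 54 at any of these powers. A level of 0.05 does, in two ways.

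**Step 3: power of the stated sample size.**

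| n per group | Two-sided 0.05 | One-sided 0.05 | Two-sided 0.5 |
|---|---|---|---|
| 54 | 70.1% | 80.2% | 96.7% |
| 57 | 72.5% | 82.1% | 97.2% |

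The 54 row is the one for the planned analysed number, since 57 × 0.95 = 54.15.

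**Step 4: what the threshold means in points.** The standard error of the difference at 54 per group is 26.9 × √(2/54) = 5.18. By the normal approximation, a two-sided level of 0.5 calls an observed difference of 0.674 × 5.18 = 3.5 points significant. At two-sided 0.05 it takes 1.96 × 5.18 = 10.1 points.

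**The case against.** The strongest reply is that any reader will take 0.5 as 0.05, so the 50% error rate will not arise in practice and this is a one-character erratum. That is probably right about conduct. It does not rescue the text: this is the only threshold in the plan, and the missing power and sidedness would remain after the digit was corrected. It is fair to say that those omissions are a lesser reporting gap and would not carry the same weight alone.

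A second reply is that 54 could have been reached by other routes. For example, two-sided 0.05 with 80% power needs 68.2 per group, and adjusting for a baseline correlation of about 0.46 reduces this to 68.2 × (1 − 0.46²) ≈ 54. That correlation is an assumption with no support in the document, but it shows that the two routes above are not exhaustive. This stands, and is a reason to ask for the inputs actually used instead of inferring them.

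A third is that the synopsis and section 6.1 call this an equivalence trial, and equivalence testing uses two one-sided tests, so sidedness cannot be finally settled here. This also stands in part. The correction is therefore limited to the difference tests that sections 9.0.2 and 9.1 describe; the equivalence margin and analysis are a separate matter.

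Finally, 0.05 is an inference. The document does not confirm it, and the authors should.

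**Conclusion.** The concern holds. Section 9.3 is wrong as written: the type I error would be about 50% per test, against 5% at P<0.05. The plan's own sample size supports reading the figure as a slip for 0.05, because 54 per group fits 0.05 and does not fit 0.5 at 80%, 90% or 95% power.

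Correcting the figure still leaves two readings of section 9.2. With 54 analysed per group, power to detect 13 points is about 70% if the test is two-sided, as 9.0.2 implies, or about 80% if it is one-sided. These figures rest on the two-sample t-test approximation with SD 26.9. This must be fixed, because it is the plan's only decision threshold.

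**What to change.** In section 9.3, replace P<0.5 with P<0.05, with the authors confirming that this was intended, and state that the difference tests in 9.1 are two-sided, in line with 9.0.2.

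In section 9.2, report the significance level, sidedness and power actually used to obtain 54 per group:

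- If the calculation was two-sided at 0.05, state that 54 analysed per group give about 70% power to detect 13 points (SD 26.9, two-sample t-test approximation), or about 73% with 57.
- If it was one-sided at 0.05 with 80% power, say so, and reconcile that with the non-directional alternative in 9.0.2 and with 9.3.
- If it used another method, such as a baseline adjustment, state the method and its inputs.

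The cost is one figure and a few words in 9.3, and one sentence in 9.2 taken from the original calculation. The correction does not require a change to the total of 114. The downside is that the stated power may prove to be about 70%; on the same approximation, 80% at two-sided 0.05 would need 69 per group before dropout. Whether 70% is acceptable is for the sponsor to decide.

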### **9.4 Criteria for the Termination of the Trial**

If the medical devices (insoles) are found to cause serious adverse events

### **9.5 Procedure for Accounting for Missing, Unused, and Spurious Data.**

If the level of missing data exceeds 5%, multiple imputation will be used to address this.

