### **9.7 Inclusion in Analysis**

All randomised participants, who have completed the trial and have not withdrawn their consent from their involvement in the trial, will be included in the analyses.

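### Section 9.5 imputes only above an undefined 5% and gives no method at or below it, where the four-visit FHSQ tests, as usually run, discard participants with one missed form

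*Combined protocol and SAP*

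**What the plan says.** Section 9.5 is a single sentence: "If the level of missing data exceeds 5%, multiple imputation will be used to address this". It does not define the denominator of the 5% (items, forms, participants or arm), the method at or below the threshold, the imputation model, the number of imputations, or how results are combined.

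Section 9.1 compares FHSQ change between groups at "baseline, 4-weeks, 8-weeks and 12-weeks". The methods are "mix methods Analysis of Variance or Friedman tests with post hoc Wilcoxon tests for within group analysis", with "Mann-Whitney U tests for between group analysis if the data are not normally distributed". The rank tests are therefore a fallback. OPUS is compared at 12 weeks only, "using unpaired t-tests or Mann-Whitney U tests if the data are not normally distributed".

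Section 9.2 gives a "required minimum sample size of 54 participants in each group plus 5% drop out rate", which makes 57 per group and 114 in total. Section 9.7 limits the analysis to "All randomised participants, who have completed the trial and have not withdrawn their consent". Under sections 6.1 and 6.4.5, the baseline FHSQ is completed face to face at the fitting visit and the other three by telephone.

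**The concern.** The observed amount of missing data decides how the primary outcome is analysed, by a rule that can be read in several ways once the data are in hand. Below the threshold the reader must infer what happens from the tests in section 9.1. A classical mixed-design ANOVA and a Friedman test both need a full row of four scores for each participant. As usually run, they remove someone who missed the week-4 call but answered at week 12.

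The stake is an avoidable loss of observed pain scores, possibly taking the analysed number below the plan's own minimum in the range where no remedy is prescribed. Above the threshold, the plan does not say how the fallback rank tests would be combined across imputed datasets.

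**Working it through.** **Inputs from the documents.** Difference 13 points and SD 26.9 (9.2); 54 per group, raised to 57 for 5% dropout, 114 in total (9.2); four FHSQ collections, three by telephone (6.1, 9.1).

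**Assumed.** Alpha 0.05, because section 9.3 prints P<0.5 and gives no sidedness; a test of difference, as sections 9.0.2 and 9.2 frame it, although the synopsis calls the trial an equivalence design; calls missed independently, with the same probability in both arms.

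**The plan's own figure.** Power is taken from the noncentral t with 2n − 2 degrees of freedom and noncentrality 13 / (26.9 × √(2/n)).
- At n = 54 the noncentrality is 2.511. Power is 80.2% one-sided and 70.1% two-sided. So 54 is reproduced by a one-sided 0.05 test with 80% power; a two-sided test with 80% power needs 69.
- The printed 0.5 with 80% power gives 7 (one-sided) or 20 (two-sided) per group, by the normal approximation, so it does not explain 54.
- Dropout: 54 / 0.95 = 56.8, rounded up to 57.

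**Participants with all three follow-up scores.** The share is (1 − m)³, where m is the chance of missing a call.
- m = 5%: 0.95³ = 0.857, so 14.3% are incomplete; 57 × 0.857 = 48.9 per arm.
- m = 2%: 0.98³ = 0.941, so 5.9% are incomplete; 57 × 0.941 = 53.6 per arm.

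**Power on the complete rows.**

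| Per arm | Noncentrality | Two-sided | One-sided |
|---|---|---|---|
| 54 | 2.511 | 70.1% | 80.2% |
| 53.6 | 2.502 | 69.8% | 80.0% |
| 49 | 2.392 | 65.8% | 76.7% |
| 46 | 2.318 | 63.0% | 74.4% |

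**What the threshold permits under different denominators.** The worst case puts each missing form in a different person.
- All forms, 114 × 4 = 456: 22 missing is 4.8% (no imputation) and 23 is 5.04%. Up to 22 people are lost, leaving (114 − 22) / 2 = 46 per arm.
- Follow-up forms, 114 × 3 = 342: 17 missing is 4.97% and 18 is 5.3%. Up to 17 people are lost, leaving 48.5 per arm.
- Participants with any missing form, 114: 5 is 4.4% and 6 is 5.3%. At most 5 are lost, leaving 54.5 per arm.

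**Where the 5%-per-call scenario falls.** It gives 342 × 0.05 = 17.1 expected missing forms. That is 3.75% of 456 (below the trigger), 5.0% of 342 (on it), or 14.3% of participants (above it). The same data can therefore lead to either analysis.

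**Can rank tests follow imputation?** A simulation pooled the Mann-Whitney effect, P(X<Y), with its variance by Rubin's rules (57 per arm, 10% missing completely at random, 20 imputations, 1,500 runs, normal data, baseline correlation 0.6, all assumed). Type I error was 5.3% at nominal 5%. Pooling is possible; the plan just gives no rule for it.

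**The case against.** The strongest reply is that nothing in the plan says participants with a missed call are dropped. The sponsor may intend a likelihood-based mixed model, which would keep them. The drop also does not apply to every named test: a single-visit Mann-Whitney, a pairwise Wilcoxon and the 12-week OPUS test lose only people missing a score that the test uses. If few calls are missed, little is lost, and if the 5% counts participants the worst case below the trigger stays above 54. All of this stands. It limits the point to the ANOVA and the Friedman test and makes its size conditional. It does not supply the missing denominator or the missing method.

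Three stronger readings are tempting but not supported.
- A reader might infer that multiple imputation cannot be used with the rank tests at all. A Mann-Whitney effect with its variance can be pooled, and chi-square statistics such as Friedman's can be combined. The rank tests also apply only if the data are non-normal.
- A reader might infer that, because planned dropout is also 5%, the trigger is about as likely as not to be crossed. That requires counting over participants with dropouts included. The denominator is undefined, and section 9.7 takes non-completers out of the analysis.
- A reader might apply the 5% miss rate to all four collections. The baseline form is completed in person at the fitting visit, so only the three calls belong in that calculation.

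It is also fair to say that defining the denominator, the method at or below 5%, the imputation model and the pooling rule would close the documented gap without a new model. That would still leave the amount of missing data choosing the analysis.

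**Conclusion.** The point holds in a limited form. Section 9.5 leaves its denominator and its method at or below 5% undefined. The four-visit ANOVA and the Friedman test, as usually run, would then discard observed scores.

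With 5% of calls missed independently and no imputation, about 49 per arm remain against 54, a loss of some 4 percentage points of power. The worst case on the all-forms count is 46 per arm. At 2% of calls missed the effect is negligible. Missed calls concentrated in the same people, as with permanent dropout, would leave fewer participants incomplete than independence implies.

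The power figures rest on an assumed alpha of 0.05 and a difference test. The loss appears for both one-sided and two-sided testing. This is an inexpensive improvement that should be made; it does not show that the trial's result would be wrong.

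**What to change.** Delete the 5% trigger. Prespecify one likelihood-based linear mixed model for repeated measures of FHSQ pain, with arm, visit, arm-by-visit interaction and baseline FHSQ pain. Fit it to every observed score whatever the amount missing. Name the week-12 between-arm difference, with its confidence interval, as the primary estimate. Align section 9.7 so that it does not remove participants whose partial scores the model can use.

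Keep multiple imputation as a sensitivity analysis, stating the imputation model, the number of imputations and the combination rule. It is most informative if it departs from missing at random, particularly for exits recorded as unable to proceed, because the FHSQ is asked only of those continuing. If any rank test is retained on imputed data, state how its results are pooled.

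The cost is SAP rewording and one standard model, with no new data, visits or participants. The downside is that the primary analysis relies on a missing-at-random assumption, which should be stated.
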